7.9. Sensitivity Analysis

A sensitivity analysis will be performed on the primary endpoint where at least six months of the duration of clinical benefit is required to be completed within the 12-month efficacy period. An additional sensitivity analysis will treat subjects who begin a new antihypertensive medication following therapeutic dosing that continues for at least 14 days as non-responders.

7.10. Statistical Software Used in Data Analysis

All data listings, tables, and figures described in this SAP will be produced using SAS®, Version 9.3 or higher. All statistical analyses described in this SAP (not including those for dosimetry) will be produced using SAS®, Version 9.3 or higher. Informal or ancillary analyses may be performed with alternate software (such as R).

8. CONCLUSION

This SAP includes a description of the pre-specified plans for key analyses of the data collected in clinical trial MIP-IB12B. Additional data analyses not described in this document will be performed on an ad hoc basis.

9. CHANGES FROM VERSION 1.0 OF SAP

The following are a summary of changes from those specified in Version 1.0 of the SAP (16 November 2009). Additional changes from Version 3.0 to 4.0 of this SAP are indicated at the end of this table.

Section	Version	Change
5.1	5.0	Clarification of handling of subjects with multiple enrollments
6	5.0	Removal of identification of per-protocol population
7.0	2.0	Time to event analyses added to statistical methods section.
7.0	5.0	Clarification of period definitions
7.2.4	2.0	New section added to reference imaging listings.
7.1	4.0	Addition of visit windows for summaries
7.3.1	2.0	Clarifications and additional details added to define algorithms for primary endpoint duration and for 50% reduction in antihypertensive medication use.
7.2.3.2	5.0	Update in MedDRA dictionary version
7.3.2	5.0	Update in WHO Drug Dictionary version
7.3.4	2.0	Listing of tumor response, clinical benefit status, and % change in CgA added.
7.3.6	2.0	Correlations between tumor change from baseline and tumor response, and among tumor markers added.
7.3.7	3.0	Section for tumor marker trend analysis deleted, all subsequent sections renumbered.
7.3.8	3.0	NIH Questionnaire reporting limited to reporting by item by visit.
7.3.9	2.0	Shift tables of pain medication use added. Comparisons of changes in potency using narcotic to NSAID conversions deleted.
7.3.11	2.0	Overall survival algorithm changed to reference date of first therapeutic dose as opposed to informed consent date.
7.3.12	2.0	New section added for site assessment of disease.
7.4.1	5.0	Definition of end of assessment period for subjects who terminate the study early, clarification of blood pressure measurements to be presented in figures by subject, clarification of clinical benefit period.
7.4.2	5.0	Added section with calculation of the primary endpoint, which was Appendix 1.
7.4.4	3.0	Threshold for reporting most frequent adverse events increased to 20% from 5%.
7.4.5	5.0	Clarification of objective tumor response criteria
7.4.7	5.0	Clarification of tumor marker analyses, change in correlation measures from percent change from baseline to tumor marker response, addition of a binary response comparison
7.4.8	5.0	Change in definition of baseline values
7.4.9	2.0	Added reporting for estimated creatinine clearance, including classification of values into estimates of renal function added.
7.4.9	2.0	Added by subject listings of nadir values by therapeutic dose for WBC, HGB, absolute neutrophils, and platelets.
7.4.9	2.0	Plots of ALT and AST deleted.
7.5.10	5.0	Clarification of summaries blood pressure results
7.5.1	5.0	Clarification of adverse event dictionary coding
7.5.5	4.0	Updated listing of hematologic adverse events
7.5.8	5.0	Clarification that final list of events may be updated
7.5.9	5.0	Addition of analysis to detect drug-induced liver injury; clarification of assessments of renal function

7.5.10	5.0	Clarification of summaries of blood pressure results and presentations of the results
7.5.11	5.0	Clarification of ECG changes of clinical importance
7.6	5.0	Clarification on date imputations
7.8	4.0, 5.0	Updated subgroup analyses
7.9	4.0, 5.0	Added sensitivity analyses
10	5.0	Added a reference
Appendix 1	5.0	Removed Appendix 1, moved to section 7.4.2
Appendix 1	5.0	Revised Appendix 1, was Appendix 2
Appendix 2	5.0	Added Appendix 2, was Appendix 3, updated with terms to be included for analysis

11. LIST OF PLANNED TABLES, LISTINGS AND FIGURES

The tables, listings and figures listed below will be prepared in accordance with the descriptions provided in this SAP.

Tables:

Table 14.1.1	Disposition (Population: Enrolled)
Table 14.1.2	Subject Characteristics (Population: Safety)
Table 14.1.3	Medical History (Population: Safety)
Table 14.1.4	Cancer History (Population: Safety)
Table 14.15	Prior Treatment for Cancer (Population: Safety)
Table 14.2.1.1A	Primary Endpoint: Decrease in Use of Antihypertensive Medications (Population: Full Analysis Set)
Table 14.2.1.1B	Primary Endpoint: Decrease in Use of Antihypertensive Medications (Population: Per Protocol Set)
Table 14.2.1.1C	Primary Endpoint: Decrease in Use of Antihypertensive Medications: Sensitivity Analysis (Population: Full Analysis Set)
Table 14.2.1.1D	Primary Endpoint: Decrease in Use of Antihypertensive Medications: Sensitivity Analysis (Population: Full Analysis Set)
Table 14.2.1.2A	Duration of Clinical Benefit (Population: Full Analysis Set)
Table 14.2.1.2B	Duration of Clinical Benefit (Population: Per Protocol Set)
Table 14.2.2.1	Tumor Response Assessment per RECIST Criteria (Population: Full Analysis Set)
Table 14.2.2.2	Tumor Response Assessment per RECIST Criteria Modified to Include Moderate Response (Population: Full Analysis Set)
Table 14.2.2.3	Tumor Response Assessment per RECIST Criteria by Primary Endpoint Status (Population: Full Analysis Set)
Table 14.2.2.4	Tumor Response Assessment per RECIST Criteria Modified to Include Moderate Response by Primary Endpoint Status (Population: Full Analysis Set)
Table 14.2.2.3	Bone Lesions (Population: Full Analysis Set)
Table 14.2.2.4	Bone Lesions: Shift from Baseline by Visit
Table 14.2.3.1	Tumor Marker Response Proportions (Population: Full Analysis Set)
Table 14.2.3.2	Tumor Marker Response Proportions by Dominant Tumor Marker (Population: Full Analysis Set)
Table 14.2.3.3	Spearman Correlation between Tumor Marker Response Proportions and relative change in tumor marker by Tumor Marker (Population: Full Analysis Set)
Table 14.2.3.4	Spearman Correlation between Tumor Marker Response Proportions & Overall Tumor Response (Population: Full Analysis Set)
Table 14.2.35	Spearman Correlation between Response Proportions & Best Overall Tumor Response (Population: Full Analysis Set)
Table 14.2.3.6	Tabulation of Best Overall Confirmed Tumor Marker Response with Best Overall Tumor Response
Table 14.2.4.1	EORTC QLQ-C30 Global Health Status/Quality of Life (Population: Full Analysis Set)
Table 14.2.4.2	EORTC QLQ-C30 Functional Scales (Population: Full Analysis Set)
Table 14.2.4.3	EORTC QLQ-C30 Symptom Scales (Population: Full Analysis Set)
Table 14.2.5A	NIH Pheochromocytoma Symptoms QOL Questionnaire: Pre Amendment 2 (Population: Full Analysis Set)
Table 14.2.5B	NIH Pheochromocytoma Symptoms QOL Questionnaire: Amendment 2 (Population: Full Analysis Set)
Table 14.2.6	Karnofsky Performance Status (Population: Full Analysis Set)
Table 14.2.7	Tumor Pain Medication Shift Table (Population: Full Analysis Set)

Table 14.2.8.1	Overall Survival (Population: Full Analysis Set)
Table 14.2.8.2	Overall Survival by Primary Endpoint Status (Population: Full Analysis Set)
Table 14.3.1.1	Treatment-Emergent Adverse Events (Population: Safety)
Table 14.3.1.1.1	Treatment-Emergent Adverse Events with Start Dates after Week 15 Following the Last Therapeutic Dose (Population: Safety)
Table 14.3.1.1.2	Treatment-Emergent Adverse Events with Start Dates after the Start of a New Anticancer Therapy but Prior to Week 15 for Subjects who Withdrew due to New Anticancer Treatment (Population: Safety)
Table 14.3.1.2	Treatment-Emergent Adverse Events by Grade (Population: Safety)
Table 14.3.1.3	Treatment-Emergent Serious Adverse Events (Population: Safety)
Table 14.3.1.4	Hematologic Serious or Grade 3/4 Adverse Events (Population: Safety)
Table 14.3.1.5	Grade 3/4 Adverse Events (Population: Safety)
Table 14.3.1.6	Adverse Events of Special Interest (AESI) (Population: Safety)
Table 14.3.2.1	Listing of Deaths During 12 Month Assessment Period (Population: Safety)
Table 14.3.2.2	Listing of Serious Adverse Events (Population: Safety)
Table 14.3.2.3	Listing of Adverse Events Leading to Drug Withdrawal (Population: Safety)
Table 14.3.2.4	Listing of Adverse Events of Special Interest (AESI) (Population: Safety)
Table 14.3.4.1.1	Change from Baseline in Hematology (Population: Safety)
Table 14.3.4.1.2	Change from Baseline in Chemistry (Population: Safety)
Table 14.3.4.1.3	Change from Baseline in Urinalysis Results (Population: Safety)
Table 14.3.4.1.4	Shifts in CTC Grade for Laboratory Parameters with Uni-Directional Criteria (Population: Safety)
Table 14.3.4.1.5	Shifts in CTC Grade for Laboratory Parameters with Bi-directional Criteria
Table 14.3.4.1.6	Incidence Rate of Post First Therapeutic Dose CTC Grade 3/4 Laboratory Values (Population: Full Analysis Set)
Table 14.3.4.1.7	Listing of Hematological Nadir Values: WBC Count (Population: Safety)
Table 14.3.4.1.8	Listing of Hematological Nadir Values: Hemoglobin (Population: Safety)
Table 14.3.4.1.9	Listing of Hematological Nadir Values: Absolute Neutrophils (Population: Safety)
Table 14.3.4.1.10	Listing of Hematological Nadir Values: Platelets (Population: Safety)
Table 14.3.4.1.11	Shifts in GFR/Creatinine Clearance
Table 14.3.5.1.1	Changes in Vital Signs (Population: Safety)
Table 14.3.5.1.2	Vital Signs Values of Potential Clinical Significance (Population: Safety)
Table 14.3.5.2.1	Changes in ECG Parameters (Population: Safety)
Table 14.3.5.2.2	ECG Values of Potential Clinical Significance (Population: Safety)
Table 14.3.5.2.3	Changes in ECG Parameters during 24-hour Holter Monitoring (Population: Safety)
Table 14.3.5.2.4	ECG Values of Potential Clinical Significance during 24-hour Holter Monitoring (Population: Safety)
Table 14.3.5.3.1	Study Drug Administration and Exposure (Population: Safety)
Table 14.3.5.3.2	Prior and Concomitant Medications (Population: Safety)

Listings:

Listing 16.2.1.1	Disposition
Listing 16.2.2.1	Inclusion Criteria
Listing 16.2.2.2	Exclusion Criteria
Listing 16.2.3.1	Subject Populations
Listing 16.2.3.2	Protocol Deviations
Listing 16.2.4.1	Demographics and Baseline Characteristics

Listing 16.2.4.2	Medical History
Listing 16.2.4.3.1	Cancer History
Listing 16.2.4.3.2	Prior Treatment for Cancer
Listing 16.2.4.4	Serum Pregnancy Test
Listing 16.2.5.1	Study Agent Administration
Listing 16.2.5.2.1	SSKI Administration
Listing 16.2.5.2.2	Inorganic Iodine Thyroid Blockade (SSKI)
Listing 16.2.6.1	Antihypertensive Medications
Listing 16.2.6.2.1	Objective Tumor Response
Listing 16.2.6.2.2.1	Objective Tumor Response and SLD by Reviewer
Listing 16.2.6.2.2.2	Lesion Status and Target Tumor Size
Listing 16.2.6.2.3.1	Antihypertensive Medication Status
Listing 16.2.6.2.3.3	Antihypertensive Medication Status and Blood Pressure Measurements
Listing 16.2.6.2.3.2	RECIST Response and % Decrease CgA
Listing 16.2.6.3.1	Organ Volume Part I
Listing 16.2.6.3.2	Organ Volume Part II
Listing 16.2.6.4	Tumor Markers
Listing 16.2.6.5	Overall Survival
Listing 16.2.6.6.1	EORTC QLQ-C30 v3 - Global Health status/Quality of Life
Listing 16.2.6.6.2	EORTC QLQ-C30 v3 - Functional Scales
Listing 16.2.6.6.3	EORTC QLQ-C30 v3 - Symptom Scales/Items
Listing 16.2.6.7.1	Quality of Life NIH Pre Amendment 2
Listing 16.2.6.7.2	Quality of Life NIH Amendment 2
Listing 16.2.6.8	Karnofsky Performance Status
Listing 16.2.6.9	Site Assessment of Disease
Listing 16.2.6.10	Tumor Pain Medications
Listing 16.2.6.11	Listing of FDG Pet Assessments
Listing 16.2.7.1.1	Adverse Events
Listing 16.2.7.1.2	Serious Adverse Events Related to Study Drug
Listing 16.2.7.2.1	Grade 3/4 Adverse Events
Listing 16.2.7.2.2	Grade 3/4 Adverse Events Related to Study Drug
Listing 16.2.7.3.3	Adverse Events of Special Interest
Listing 16.2.7.3	Adverse Events with Severity of 'Fatal' or Outcome of 'Death'
Listing 16.2.8.1.1	Hematology Part 1
Listing 16.2.8.1.2	Hematology Part 2
Listing 16.2.8.1.3	Chemistry Part 1
Listing 16.2.8.1.4	Chemistry Part 2
Listing 16.2.8.1.5	Chemistry Part 3
Listing 16.2.8.1.6	Chemistry Part 4: Thyroid Function Test
Listing 16.2.8.1.7	Urinalysis Part 1
Listing 16.2.8.1.8	Urinalysis Part 2
Listing 16.2.8.1.9	GFR/Creatinine Clearance
Listing 16.2.8.1.10	Subjects who met Hy's Law Criteria
Listing 16.2.8.2.1	Vital Signs
Listing 16.2.8.2.2	Blood Pressure Measurements

Listing 16.2.8.2.2a	Blood Pressure Measurements from Vital Signs
Listing 16.2.8.3.1	Quantitative ECG Parameters
Listing 16.2.8.3.2	Qualitative ECG Parameters
Listing 16.2.8.3.3	Quantitative ECG Parameters during 24-hour Holter Monitoring
Listing 16.2.8.3.4	Qualitative ECG Parameters during 24-hour Holter Monitoring
Listing 16.2.8.3.5	New ECG Abnormalities noted on 24-hour Holter Monitoring
Listing 16.2.8.4.1	Physical Examination
Listing 16.2.8.5.1	Concomitant and Prior Medications, Excluding Antihypertensives
Listing 16.2.8.5.2	Analgesic Medications (excluding Tumor Pain Medications)

Figures:

Figure 1A-1xx	Blood Pressure Measurements and Antihypertensive Medication Use (by subject) Healthcare Provider Measurements
Figure 1B-1xx	Blood Pressure Measurements and Antihypertensive Medication Use (by subject) – Subject Measurements
Figure 2	Duration of Reduction in Antihypertensive Use of $\geq 50\%$
Figure 3	Waterfall Plot of Best Percent Change in Sums of Longest Diameters of Tumor Target Lesions
Figure 4	Karnofsky Performance Status over Time
Figure 5	Overall Survival
Figure 6	Common Adverse Events
Figure 7	Absolute Neutrophils over Time by Subject
Figure 8	Platelet Count over Time by Subject

APPENDIX 1. VISIT WINDOWS

These windows are intended for data summaries by time point. When multiple assessments fall within a window, the assessment closest to the nominal time will be used in summaries. If there are multiple visits equally distant from the midpoint of a window, then the earlier visit will be used.

Efficacy Assessments

No	End Point	From Imaging Dose 1	From Therapeutic Dose 1	From Therapeutic Dose 2
1	Overall Tumor Response (CT/MRI Scans)	Screening / Baseline (Day -28 to Day 0)	Month 3 (Day 81 - Day 101) Month 6 (Day 173 - Day 193) Month 9 (Day 264 - Day 284) Month 12 (Day 355 - Day 375) Month 18 (Day 518 - Day 578) Month 24 (Day 700 - Day 760) Month 30 (Day 883 - Day 943) Month 36 (Day 1065 - Day 1125) Month 42 (Day 1248 - Day 1308) Month 48 (Day 1430 - Day 1490) Month 54 (Day 1613 - Day 1673) Month 60 (Day 1795 - Day 1855)	
2	Tumor Markers	Screening / Baseline (Day -28 to Day 0)	Week 2 (Day 8 - Day 14) Week 4 (Day 22 - Day 28) Week 6 (Day 36 - Day 42) Week 8 (Day 50 - Day 56) Week 10 (Day 64 - Day 70) Week 12 (Day 78 - Day 84) Week 14 (Day 92 - Day 98) Week 16 (Day 106 - Day 112) Week 18 (Day 120 - Day 126) Week 20 (Day 134 - Day 140) Week 22 (Day 148 - Day 154) Week 24 (Day 162 - Day 168) Month 7 (Day 203 - Day 223)	

No	End Point	From Imaging Dose 1	From Therapeutic Dose 1	From Therapeutic Dose 2
			Month 8 (Day 233 - Day 253) Month 9 (Day 264 - Day 284) Month 10 (Day 294 - Day 314) Month 11 (Day 325 - Day 345) Month 12 (Day 355 - Day 375) Month 18 (Day 518 - Day 578) Month 24 (Day 700 - Day 760) Month 30 (Day 883 - Day 943) Month 36 (Day 1065 - Day 1125) Month 42 (Day 1248 - Day 1308) Month 48 (Day 1430 - Day 1490) Month 54 (Day 1613 - Day 1673) Month 60 (Day 1795 - Day 1855)	
3	Soloway Score (Bone Scan) and optional FDG-PET Scan	Screening / Baseline (Day -28 to Day 0)	Month 3 (Day 81 - Day 101) Month 6 (Day 173 - Day 193) Month 9 (Day 264 - Day 284) Month 12 (Day 355 - Day 375)	
4	Karnofsky Performance	Screening / Baseline (Day -28 to Day 0)	Day 1 Week 6 ± 10 days (Day 32 - Day 52) Month 3 (Day 81 - Day 101) Month 6 (Day 173 - Day 193) Month 9 (Day 264 - Day 284) Month 12 (Day 355 - Day 375)	Day 1 Week 6 ± 10 days (Day 32 - Day 52)
5	Symptom Response (NIH Pheochromocytoma Clinical Questionnaire) and EORTC QLQ-30 Questionnaire	Screening / Baseline (Day -28 to Day 0) Note: two assessments are to be performed prior to the first therapeutic dose within this window	Week 3 (Day 15 - Day 21) Week 6 (Day 36 - Day 42) Week 10 (Day 64 - Day 70) Week 12 (Day 78 - Day 84) Week 15 (Day 99 - Day 105) Week 18 (Day 120 - Day 126) Week 22 (Day 148 - Day 154) Month 6 (Day 173 - Day 193) Month 7 (Day 203 - Day 223) Month 8 (Day 233 - Day 253)	

No	End Point	From Imaging Dose 1	From Therapeutic Dose 1	From Therapeutic Dose 2
			Month 9 (Day 264 - Day 284) Month 10 (Day 294 - Day 314) Month 11 (Day 325 - Day 345) Month 12 (Day 355 - Day 375)	
6	Tumor Pain Medication		Month 3 (Day 81 - Day 101) Month 6 (Day 173 - Day 193) Month 9 (Day 264 - Day 284) Month 12 (Day 355 - Day 375)	

Safety Assessments

No	End Point	From Imaging Dose 1	From Therapeutic Dose 1	From Therapeutic Dose 2
1	Vital Signs (pulse, temperature, respiration)	Screening / Baseline (Day -28 to Day 0) Day 1: 4 hours prior Day 1: 4 hours post	Day 1: 4 hours prior Day 1: 4 hours post	Day 1: 4 hours prior Day 1: 4 hours post
2	Vital Signs (body weight)	Day 1: prior to dosing	Day 1: prior to dosing	Day 1: prior to dosing
3	Vital Signs (BP and heart rate by Health Staff and Subject Readings)	Screening / Baseline (Day -28 to Day 0) Day 1: 4 hours prior Day 1: 4 hours post	Day 1: 4 hours prior Day 1: 4 hours post Week 1 (Day 2 - Day 7) 2x week Week 2 (Day 8 - Day 14) 2x week Week 3 (Day 15 - Day 21) 2x week Week 4 (Day 22 - Day 28) 2x week Week 5 (Day 29 - Day 35) 2x week Week 6 (Day 36 - Day 42) 2x week Week 7 (Day 43 - Day 49) Week 8 (Day 50 - Day 56) Week 9 (Day 57 - Day 63) Week 10 (Day 64 - Day 70) Week 11 (Day 71 - Day 77)	Day 1: 4 hours prior Day 1: 4 hours post Week 1 (Day 2 - Day 7) 2x week Week 2 (Day 8 - Day 14) 2x week Week 3 (Day 15 - Day 21) 2x week Week 4 (Day 22 - Day 28) 2x week Week 5 (Day 29 - Day 35) 2x week Week 6 (Day 36 - Day 42) 2x week Week 7 (Day 43 - Day 49) Week 8 (Day 50 - Day 56) Week 9 (Day 57 - Day 63) Week 10 (Day 64 - Day 70) Week 11 (Day 71 - Day 77)

No	End Point	From Imaging Dose 1	From Therapeutic Dose 1	From Therapeutic Dose 2
			Week 12 (Day 78 - Day 84) Week 13 (Day 85 - Day 91) Week 14 (Day 92 - Day 98) Week 15 (Day 99 - Day 105) Week 16 (Day 106 - Day 112) Week 17 (Day 113 - Day 119) Week 18 (Day 120 - Day 126) Week 19 (Day 127 - Day 133) Week 20 (Day 134 - Day 140) Week 21 (Day 141 - Day 147) Week 22 (Day 148 - Day 154) Week 23 (Day 155 - Day 161) Week 24 (Day 162 - Day 168) Month 7 (Day 203 - Day 223) Month 8 (Day 233 - Day 253) Month 9 (Day 264 - Day 284) Month 10 (Day 294 - Day 314) Month 11 (Day 325 - Day 345) Month 12 (Day 355 - Day 375)	Week 12 (Day 78 - Day 84) Week 13 (Day 85 - Day 91) Week 14 (Day 92 - Day 98) Week 15 (Day 99 - Day 105) Week 16 (Day 106 - Day 112) Week 17 (Day 113 - Day 119) Week 18 (Day 120 - Day 126) Week 19 (Day 127 - Day 133) Week 20 (Day 134 - Day 140) Week 21 (Day 141 - Day 147) Week 22 (Day 148 - Day 154) Week 23 (Day 155 - Day 161) Week 24 (Day 162 - Day 168)
4	ECG and 24-Hour Holter Monitoring	Day 1: 2 hours prior (triplicate ECG) up to 2 minutes post 10 ± 2 minutes post 15 ± 2 minutes post 20 ± 2 minutes post within 15 minutes prior to imaging scans 2 and 3	Day 1 (24-hr Holter monitoring to begin between 100 to 45 minutes prior to dosing and to continue for approximately 23 hours following dosing) Week 1 (Day 2 - Day 8)	Day 1 (24-hr Holter monitoring to begin between 100 to 45 minutes prior to dosing and to continue for approximately 23 hours following dosing) Week 1 (Day 2 - Day 8)
5	Hematology, Chemistry & Urine Analysis	Screening / Baseline (Day -28 to Day 0) Day 1 within 24 hr prior	Day 1 within 24 hr prior Week 2 (Day 8 - Day 14) Week 3 (Day 15 - Day 21)	Day 1 within 48 hr prior Week 2 (Day 8 - Day 14) Week 3 (Day 15 - Day 21)

No	End Point	From Imaging Dose 1	From Therapeutic Dose 1	From Therapeutic Dose 2
			Week 4 (Day 22 - Day 28) Week 5 (Day 29 - Day 35) Week 6 (Day 36 - Day 42) Week 7 (Day 43 - Day 49) Week 8 (Day 50 - Day 56) Week 9 (Day 57 - Day 63) Week 10 (Day 64 - Day 70) Week 11 (Day 71 - Day 77) Week 12 (Day 78 - Day 84) Week 13 (Day 85 - Day 91) Week 14 (Day 92 - Day 98) Week 15 (Day 99 - Day 105) Week 16 (Day 106 - Day 112) Week 17 (Day 113 - Day 119) Week 18 (Day 120 - Day 126) Week 19 (Day 127 - Day 133) Week 20 (Day 134 - Day 140) Week 21 (Day 141 - Day 147) Week 22 (Day 148 - Day 154) Week 23 (Day 155 - Day 161) Week 24 (Day 162 - Day 168) Month 7 (Day 203 - Day 223) Month 8 (Day 233 - Day 253) Month 9 (Day 264 - Day 284) Month 10 (Day 294 - Day 314) Month 11 (Day 325 - Day 345) Month 12 (Day 355 - Day 375)	Week 4 (Day 22 - Day 28) Week 5 (Day 29 - Day 35) Week 6 (Day 36 - Day 42) Week 7 (Day 43 - Day 49) Week 8 (Day 50 - Day 56) Week 9 (Day 57 - Day 63) Week 10 (Day 64 - Day 70) Week 11 (Day 71 - Day 77) Week 12 (Day 78 - Day 84)
6	Renal Function	Screening / Baseline (Day -28 to Day 0)	Month 6 (Day 173 - Day 193) Month 12 (Day 355 - Day 375)	
7	TSH, T3, T4	Screening / Baseline (Day -28 to Day 0)	Month 12 (Day 355 - Day 375)	

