11.3 Screening / Baseline

All subjects will be screened to ensure that all inclusion and exclusion criteria are met. Baseline procedures (detailed in Section 11.5 below) include a medical history, physical examination, measurement of vital signs, CT or MR scans, bone scans, FDG scans (if available), laboratory tests and completion of quality of life questionnaires. If the subject has not been assessed for renal function through either a 24 hour urine creatinine clearance or Glomerular Filtration Rate (GFR using ^{99m}Tc diethylenetriaminepentaacetic acid (DTPA) analysis) within four weeks of screening, one of these procedures will be performed during the screening/baseline period. A serum pregnancy test for all females of childbearing potential will be performed following informed consent and prior to each administration of study drug. Renal volume will be obtained. An assessment of tumor markers, blood pressure and heart rate will be performed during the baseline/screening period. If Screening/Pre-Screening procedures are completed as standard of care within 48 hours prior to obtaining informed consent, these procedures do not need to be repeated as Screening assessments specifically for this study. The data from these assessments will be collected in the appropriate CRF location.

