11.5.5 Laboratory Evaluation of Renal Function

Either a 24 hour urine creatinine clearance or Glomerular Filtration Rate (GFR using ^{99m}Tc diethylenetriaminepentaacetic acid [DTPA] analysis) will be assessed for all subjects who have not had one of these assessments within four weeks of screening/baseline. Additionally, for all subjects, renal function will be assessed at the Month 6 and 12 Efficacy Visits using the same methodology used to evaluate renal function at screening/baseline.

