Concomitant Medications			Concomitant	Concomitant medications taken throughout the study will be recorded	throughout the stu	dy will be recor	ded		
Hematology, Chem, UA ⁵	Х	Х	Х		Week 2-Week 24	Х	1x month (Months 7-12)		
TSH, T3, T4	Х							X (Month 12 ONLY)	

MIP-IB12B_CSP_V1a3_21Mar2014 CONFIDENTIAL

Ultratrace Iobenguane I 131 Protocol No. MIP-IB12B	31	APPENDIX	VII: SCHED	DIX VII: SCHEDULE OF PROCEDURES	DCEDURES			Pheochro Page 97	Pheochromocytoma Page 97
	Screening/ Baseline	Imaging Dose/ Scans	Therapeutic Doses	Ultratrace I 131 Scan	Post Therapy I	Post Each Therapy	Post Therapy I	y I	Long Term Follow Up* Every 6 mo
Procedure/Test	Week -4 to Imaging Dose	Imaging Dose within 30 days of therapeutic dose	Day 0 and Month 3*	Within 7 days after each therapeutic dose	Weekly through 24 Weeks	6 weeks after each therapy	Monthly post 1 st Therapy	3, 6, 9 ,12 Months post 1st Therapy	Years 2 through 5 after 1st Therapy
Renal function (GFR or 24 hr $CC)^6$	Х							Month 6 & 12	
Renal Volume	Х								
Tumor Markers	X				Every 2 weeks during weeks 2-24		1x month (Months 7-12)		X
Pregnancy Test, serum or urine(if applicable)	X (serum)	X (urine, within 48hrs prior to dose)	X (urine, within 48 prior to dose)						
CT or MR Scan of chest, pelvis and abdomen ^{7}	Х							X	Х
Optional FDG scan	Х							Х	
Bone Scan ⁸	X							X^8	
ECG ⁹		Х		Х					
Holter Monitor (24 hours) ¹⁰			Х						
SSKI Administration ¹¹		X (Day -2 to Day 0)	Х						
Imaging Dose 3 to 6 mCi Ultratrace I 131		Х							
Imaging Scans Ultratrace I 131 ¹² (scintigraphic)		X (3)		Х					
Dosimetry Calculation for Therapy Dose		X (Day -2 to Day 0)							
Therapeutic Dose Ultratrace I 131			X(dose 1 on day 0 and dose 2 on Month 3)						
EORTC QLQ-C30 ^{13/} NIH Pheo Clinical Questionnaire ¹³	X (2)				Week 3,6,10,12,15, 18,22		Monthly Months 6- 12		

MIP-IB12B_CSP_V1a3_21Mar2014 CONFIDENTIAL

MIP-IB12B_CSP_V1a3_21Mar2014 CONFIDENTIAL

I 131	2B
enguane]	MIP-IB12B
obeng	, ,
	l No.
tratrace]	rotocol
Π	Ě

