7.1. Visit Windows and Relative Days

The complete list of visit windows used throughout the study is provided in [Appendix 1](#).

For efficacy summary tabulations, the visit windows will be used as they apply to the evaluation schedule for each endpoint. In the case of multiple visits per reporting window, the visit closest to the midpoint of the interval will be used for summary assessments. If there are multiple visits equally distant from the midpoint of a window, then the earlier visit will be used. These windows apply to, tumor response, bone scans, site assessment of disease, and Karnofsky performance status tumor markers.

For safety tabulations, day of measurement is computed relative to date of each dose until the next dose occurs, for example prior to the first therapeutic infusion until the second therapeutic infusion occurs, then relative to the second therapeutic infusion. These windows apply to ECGs, vital signs and labs. The visit windows for each assessment (vital signs, ECGs, laboratory tests) are specified in [Appendix 1](#) as the scheduled evaluations vary by assessment.

ECGs will be obtained and summarized for readings within 15 minutes prior to the second and third imaging scans as well as those obtained within seven days following each therapeutic dose.

Vital signs will be summarized for readings 4 hours prior and 4 hours post each dose.

Laboratory results taken within 24 hours post imaging and first therapeutic dose and 48 hours post second therapeutic dose will be summarized in addition to those visits where the assessment are scheduled.

Relative days:

The following relative days will be computed for subjects:

For all subjects and visit dates, compute SDAY (Study day) as assessment date minus informed consent date + 1.

For subjects with at least one dose and visit dates:

- TDAYDOS1 (Treatment day from 1st dosimetry) as assessment date minus date of first dosimetry dose + 1.
- TDAYDOS2 (Treatment day from 2nd dosimetry) as assessment date minus date of second dosimetry dose + 1 for any subjects who received a second dosimetry dose.
- TDAYTX1 (Treatment day from therapeutic dose 1) as assessment date minus date of first therapeutic dose + 1; missing for subjects with only a dosimetry dose.
- TDAYTX2 (Treatment day from therapeutic dose 2) as assessment date minus date of second therapeutic dose + 1; missing for subjects with only 1 therapeutic dose and also for subjects with only a dosimetry dose.

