7.4.8. Symptom Response/Quality of Life

A symptom response instrument will be used to evaluate symptoms specific to NIH Quality of Life and Symptoms Questionnaire for Pheochromocytoma and Paraganglioma. The questionnaire is administered twice during the baseline period prior to the first therapeutic dose. The results of the two responses will be averaged by item and will be treated as the baseline values. Results by item will be summarized for the Full Analysis Set, and questionnaire data will be listed.

The EORTC QLQ-C30 v.3^[3] will be used to evaluate QoL. The questionnaire is administered twice during the baseline period prior to the first therapeutic dose. The last non-missing values obtained closest to dosing will be treated as the baseline values. The results of QoL and changes from baseline will be summarized by visit and domain across the Full Analysis Set and will be listed. This data will be summarized as follows: Global Health Status/Quality of Life, Functional Scales, and Symptom Scales. The best response within 12 months after first therapeutic dose will also be reported.

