An estimated creatinine clearance may be calculated based on serum creatinine, urine creatinine and urine volume. Serum creatinine values within 7 days prior to urine collection may be combined with the urinalysis parameters. Renal function based on estimated creatinine clearance values will be categorized as normal (≥90 ml/min), mild decrease in GFR (60-89 ml/min), moderate decrease in GFR (30-59 ml/min), severe decrease in GFR (15-29 ml/min) and end stage renal disease (<15 ml/min not on dialysis or requiring dialysis). A shift table of creatinine clearance from Baseline to the 12-month endpoint will be provided.

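### The SAP's renal-function baseline window (Day -28 to Day 0) is narrower than the prior test the protocol accepts, so some subjects could have no baseline for the GFR/clearance shift table

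*SAP*

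**What the plan says.** SAP Appendix 1, Safety Assessments row 6 (Renal Function), gives the baseline window as "Screening / Baseline (Day -28 to Day 0", in the column counted from Imaging Dose 1. The appendix states its purpose: "These windows are intended for data summaries by time point". SAP 7.1 refers to these windows for the safety tabulations, including laboratory results. SAP 7.5.9 then plans the analysis that needs the baseline: "A shift table of creatinine clearance from Baseline to the 12-month endpoint will be provided". The list of tables carries it as Table 14.3.4.1.11.

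The protocol sets the timing of the test itself. Under 11.3, if the subject has had no 24-hour clearance or GFR "within four weeks of screening, one of these procedures will be performed during the screening/baseline period". Under 11.5.5, one of the two tests "will be assessed for all subjects who have not had one of these assessments within four weeks of screening/baseline". A subject with a recent enough prior test is therefore not retested. The Schedule of Procedures (Protocol Appendix VII) places screening at "Week -4 to Imaging Dose".

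**The concern.** The protocol allowance and the SAP window are both four weeks long but are counted from different dates. The protocol counts back from screening and the SAP counts back from the Imaging Dose. Whenever screening comes well before the Imaging Dose, a test that met the protocol can lie before the SAP window opens, and the protocol asks for no second test to fill it.

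The mismatch arises from the renal waiver. For screening procedures in general, Protocol 11.3 lets standard-of-care results stand only if done within 48 hours before consent. Renal function alone is given four weeks, yet row 6 carries the same window as thyroid function in row 7.

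The SAP states a baseline rule for several other measures. For the EORTC questionnaire, for example: "The last non-missing values obtained closest to dosing will be treated as the baseline values". It also states one for the NIH questionnaire, the ECGs and the antihypertensive doses. It states none for GFR or clearance beyond the window.

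At stake is the completeness of the only planned summary table of GFR or clearance, in a trial whose protocol calls renal toxicity a key concern when describing the earlier dosimetry study (7.6.1). A subject with a valid pre-treatment value and a valid Month 12 value could go uncounted because of how days are numbered.

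**Working it through.** The plan gives no figure to reproduce; the check is date arithmetic.

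**Inputs**
- t = days from the accepted prior test to screening, 0 to 28 (Protocol 11.3, 11.5.5).
- s = days from screening to the Imaging Dose, up to 28 (Schedule of Procedures).
- Window: Day -28 to Day 0 from Imaging Dose 1 (SAP Appendix 1, row 6).
- Day count: "TDAYDOS1 (Treatment day from 1st dosimetry) as assessment date minus date of first dosimetry dose + 1" (SAP 7.1).

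**Earliest accepted test**
- Age at the Imaging Dose = s + t, at most 28 + 28 = 56 days.
- SAP day = -(s + t) + 1 = -56 + 1 = Day -55. As a plain difference it would be Day -56.
- That is 55 - 28 = 27 days before the window opens (28 days by plain difference).

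**When an accepted test falls outside the window**
- By the SAP day count: -(s + t) + 1 < -28, so s + t ≥ 30.
- By plain difference: -(s + t) < -28, so s + t ≥ 29.

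| Screening, days before Imaging Dose (s) | Out of window if t is at least (SAP count) | Share of t = 0 to 28 | Plain difference |
|---|---|---|---|
| 1 | none | 0/29 = 0% | 1/29 = 3% |
| 7 | 23 | 6/29 = 21% | 7/29 = 24% |
| 14 | 16 | 13/29 = 45% | 14/29 = 48% |
| 21 | 9 | 20/29 = 69% | 21/29 = 72% |
| 28 | 2 | 27/29 = 93% | 28/29 = 97% |

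Over all 28 × 29 = 812 combinations (s = 1 to 28, t = 0 to 28), 378/812 = 47% fall outside by the SAP count and 406/812 = 50% by plain difference. These are shares of date combinations, weighted evenly by assumption. They are not shares of subjects.

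**From dates to subjects**

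Share of all subjects without a windowed baseline = w × p, where w is the share relying on a prior test and p is the share of those tests that fall out of window. The documents give neither. If w were 10% to 40% and p were 21% to 69% (the s = 7 to s = 21 rows), the product would run from 0.10 × 0.21 = 2% to 0.40 × 0.69 = 28%. If few subjects used the waiver, or used it only with recent tests, it would be near zero.

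**Check of the fix**

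With no lower day bound, none of the 812 combinations is excluded.

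**The case against.** The strongest reply is that nothing in the SAP says an out-of-window value is discarded. Appendix 1 and 7.1 say which value to choose when several fall in a window; they do not say that an accepted pre-treatment value outside it becomes missing. SAP 7.6 says in general terms that all available safety data are tabulated. Protocol 11.5.5 requires the Month 6 and Month 12 tests to use the same method as the screening/baseline evaluation, for every subject, so the protocol evidently treats the accepted test as the baseline. A programmer could reasonably use it.

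This stands as a limit on the consequence. A reader might infer that these subjects will be dropped and the renal denominator will shrink. The documents support only that this could happen if the window is applied strictly. The reply does not remove the mismatch: 7.6 gives no renal baseline rule, and the one stated window excludes the older test.

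Three further points:

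- Section 11.5.5 counts from screening/baseline, which is a period, whereas 11.3 counts from screening. The eight-week figure follows most clearly from 11.3. The text of footnote 6 to the renal row of the Schedule was not available for this review and might narrow the interval; it should be checked.
- SAP 7.5.9 permits 24-hour urine creatinine when GFR or clearance was not reported, and an estimated clearance from serum creatinine, urine creatinine and urine volume. Screening includes serum creatinine and a 24-hour urine collection for tumor markers. This could supply an in-window value, but the documents do not say that urine creatinine was measured on that collection.
- Renal safety does not rest on this table alone. Serum creatinine and urea nitrogen are among the chemistry results summarized as change from Screening. GFR and clearance have their own listing (16.2.8.1.9). Elevated creatinine and renal dysfunction are adverse events of special interest in SAP Appendix 2.

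**Conclusion.** The point holds in a limited, conditional form. The SAP's renal baseline window does not cover every test the protocol accepts as baseline. By the SAP's own day count, an accepted test can be as early as Day -55, against a window that opens at Day -28. If the window is applied as written, a subject with such a test could be left out of Table 14.3.4.1.11.

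Two assumptions carry this: that the four weeks in 11.3 are counted back from a screening date that may itself be four weeks before the Imaging Dose, and that the window is used to select the baseline for the shift table.

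Two stronger readings are not supported. A reader might take the percentages above as an expected loss of subjects, but the documents give no rate of use of the waiver and no distribution of test dates. A reader might also infer that renal safety would go unassessed, but individual values stay in the listing and the other renal summaries remain. The effect is confined to one descriptive safety table and does not reach the primary analysis or any hypothesis test.

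**What to change.** In SAP Appendix 1, Safety Assessments row 6, replace the renal baseline window with a rule: baseline is the last GFR or creatinine-clearance result before the Imaging Dose that was accepted under Protocol 11.3 or 11.5.5, with no fixed lower day bound. Flag results older than Day -28 in Listing 16.2.8.1.9. Leaving out a lower bound also avoids having to choose between Day -55 and Day -56.

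The cost is one line of SAP wording and a listing flag, with no new data. The downside is that some baselines will be up to about eight weeks old at the Imaging Dose, which the protocol already accepts; the flag lets a reader see which ones.
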